3. STUDY DESIGN

3.1 General Design

A randomized controlled trial to determine the effect of gabapentin enacarbil on opioid consumption and pain scores in patients having primary hip or knee replacement surgery with spinal anesthesia. Randomization will be web-based and stratified by type of surgery. Allocation will be concealed until shortly before drug/placebo administration.

Participating patients will be randomly assigned to standard management with GEN or to standard management with placebo. Patients will be given GEN 600 mg bid or placebo 600 mg bid for 1 preoperative day and will receive 600 mg GEN or placebo about 2 hours before surgery and then restarted on GEN or placebo 600 mg within 6 hours of surgery, and then 600 mg bid for three additional days.

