5.3 Method for Assigning Subjects to Treatment Regimen

Participating patients will be randomly assigned to gabapentin enacarbil or placebo. Randomization will be web-based through REDCap and stratified by type of surgery. Allocation will be concealed until shortly before drug/placebo administration. Randomization will be stratified by type of surgery (hip versus knee). Randomization codes will be web based using random-sized blocks, and treatment assignment (gabapentin enacarbil or placebo) will be done using a password-protected website administered by the Department of Outcomes Research statistical team at Cleveland Clinic.

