7.2 Statistical Methods

The modified intention-to-treat approach will be utilized: patients who were randomized, had the procedure and received any amount of treatment will be included in the analysis. The per-protocol analysis (on patients who were randomized, had the procedure and followed the treatment regimen at least 50% of the times) will be conducted for the primary outcome as a sensitivity analysis.

First, randomized groups will be compared for balance on potentially confounding baseline demographic and preoperative variables using descriptive statistics.

Primary outcome. In the primary hypothesis, quality of postoperative analgesia will be characterized using both pain scores and total postoperative opioid consumption within 72 hours of the surgery or till discharge. We will consider gabapentin enacarbil group better than placebo group on the postoperative pain management if gabapentin enacarbil group is found noninferior (i.e., not worse) on both outcomes and superior on at least one of the outcomes. We define the a-priori noninferiority pain score delta as 1 point and the opioid delta as 1.1 for the ratio in geometric

means IV morphine equivalent doses (meaning 10% difference between group's median doses). Thus, our primary hypothesis will be assessed in a joint hypothesis-testing framework described by Mascha and Turan (42).

We will first estimate confidence intervals for the treatment effect for both pain score and opioid consumption. Assuming lognormal distribution of opioid consumption, we will evaluate the percent difference in geometric mean IV morphine equivalent dose between the two groups using a log-linear regression model. To evaluate the difference in mean pain scores we will first summarize the pain scores by computing time weighted average (TWA) pain score for each patient. Then we will use a linear regression model to assess the treatment effect on the TWA pain scores.

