Our joint hypothesis testing will consist of two steps. First, we will evaluate the noninferiority of gabapentin enacarbil to placebo group on both outcomes. Noninferiority (being “not worse”) of gabapentin enacarbil group will be concluded for both outcomes at the significance level of 0.025 if the upper limit of 95% confidence interval is below the corresponding noninferiority delta. Second, if noninferiority is concluded for both pain scores and opioid consumption, we will proceed to a 1-tailed superiority test on each outcome in the same direction as the noninferiority testing. Superiority testing will be done at the overall 0.025 significance level and will be adjusted for multiple testing (two outcomes) via Bonferroni correction ($0.025/2=0.0125$); superiority will thus be claimed for a particular outcome if the 97.5% confidence interval is below zero (below one for ratio in geometric means for opioid). Overall Type I error rate for the joint hypothesis testing will be maintained at 0.025 (we choose 0.025 instead of 0.05 because we have to consider treatment effect both directions gabapentin enacarbil vs. placebo and placebo vs. gabapentin enacarbil) even though both noninferiority and superiority will be tested at the 0.025 level. This is because noninferiority on both outcomes and superiority on at least one is required to claim gabapentin enacarbil group better than placebo group, and thus the joint hypothesis framework is an intersection-union test (which does not require additional adjustment for testing two sets of hypotheses).

In addition to the confidence intervals, tests giving the P-values for noninferiority and superiority will be performed. For noninferiority, two 1-tailed t-tests for each outcomes will be done to assess whether the difference in means pain scores (or ratio in geometric means for opioid) is below the given delta (log of given delta for opioid). For superiority, two 1-tailed t-tests will be done in the same direction as the noninferiority testing to assess whether the difference in means pain scores (or ratio in geometric means for opioid) is below zero (one). Estimates of treatment effect and standard error will be based on the regression models described above. .

Secondary outcomes. We will compare two randomized groups on each secondary outcome using appropriate 2-tailed tests for superiority: t-tests or Wilcoxon rank sum tests for continuous outcomes as of duration of hospitalization and QoR-15 satisfaction score.

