To assess if administration of gabapentin enacarbil decreases the incidence of nausea and vomiting within initial 72 hours of the surgery and the risk of pain conversion from acute to chronic chi-square tests will be used.

The significance level for the set of secondary outcomes will be preserved at 0.05 overall by using a criterion of $P < 0.05/4 = 0.0125$ for each test (applying a Bonferroni correction for multiple testing of the 4 secondary outcomes).

R statistical software version 2.12.1 (The R Foundation for Statistical Computing, Vienna, Austria)

and SAS statistical software version 9.3 (SAS Institute, Cary, NC, USA) for 64-bit Microsoft Windows will be used for all statistical analysis.

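### Secondary outcomes are tested without the hip/knee stratum used at randomisation, so the tests are conservative and lose power if hip and knee patients differ

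*Combined protocol and SAP*

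**What the plan says.** Section 3.1 of the combined protocol and SAP states: "Randomization will be web-based and stratified by type of surgery". Section 5.3 repeats this, names hip and knee as the strata, and adds random-sized blocks.

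Section 7.2, under secondary outcomes, opens with "We will compare two randomized groups on each secondary outcome using appropriate 2-tailed tests for superiority". It then gives "t-tests or Wilcoxon rank sum tests for continuous outcomes", which are length of stay and QoR-15. For postoperative nausea and vomiting and for persistent pain at three months it says "the risk of pain conversion from acute to chronic chi-square tests will be used". Each of the four outcomes is judged by "using a criterion of $P < 0.05/4 = 0.0125$ for each test".

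No section puts surgery type into a secondary analysis. None says which of the two continuous tests applies to which outcome, or when that is decided. The primary analysis does not settle it by analogy: for pain, "we will use a linear regression model to assess the treatment effect on the TWA pain scores", with no covariate named.

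**The concern.** Stratified blocks make the hip/knee mix nearly equal in the two arms, so a difference between hip and knee patients hardly moves the treatment contrast. An unstratified test still estimates its error from all patients in an arm together, and that spread includes the hip/knee difference. The standard error is then larger than the design warrants. The test rejects too rarely under the null and misses more real effects.

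Length of stay and QoR-15 could plausibly differ between hip and knee. With 100 patients and a per-test level of 0.0125, the secondary aims have little power to give away.

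The either/or wording for the two continuous outcomes is a smaller, separate gap. It leaves the test open until the data are in hand.

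**Working it through.** **Inputs from the documents.** 50 patients per arm (7.1); four secondary outcomes at two-sided 0.0125 each (7.2); strata hip and knee (5.3).

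**Assumptions, because the documents give no figures.** Hip/knee difference d of 0.5 to 1 within-stratum SD; treatment effect 0.6 SD; normal outcome; even hip/knee split in each arm.

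**1. The plan's own figure.** 0.05/4 = 0.0125. Four such tests sum to 0.05; if independent, 1 − (1 − 0.0125)^4 = 0.049. The figure is right as stated.

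**2. Continuous outcomes.** With strata balanced, the true standard error of the arm difference is √(2/50) = 0.20 within-stratum SD. The unstratified t-test estimates a variance of about 1 + d²/4 instead of 1, so its standard error is too large by k = √(1 + d²/4).

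- d = 0.5: k = √1.0625 = 1.031
- d = 1: k = √1.25 = 1.118

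The critical value of t (98 df, two-sided 0.0125) is 2.545. On the correct scale the test therefore demands 2.545 × 1.031 = 2.62, or 2.545 × 1.118 = 2.85. The noncentrality for 0.6 SD is 0.6/0.20 = 3.0. Tail areas of the t and noncentral t give:

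| Hip/knee difference | True level, unstratified | Power, unstratified | Power, surgery type included |
|---|---|---|---|
| 0 | 0.0125 | 67.5% | 67.5% |
| 0.5 SD | 0.010 | 64.7% | 67.5% |
| 1 SD | 0.005 | 56.3% | 67.5% |

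Simulation agrees. Over separate runs of 20,000 and 40,000 trials the unadjusted level was 0.0103 and 0.0106 at 0.5 SD, and 0.0049 and 0.0058 at 1 SD. The adjusted level stayed at about 0.012 to 0.014. Simulated power at 0.6 SD was about 64 to 65% (0.5 SD) and 56 to 57% (1 SD), against 67 to 68% adjusted. For a 0.7 SD effect, power rises with adjustment from 80.7% to 82.9% at 0.5 SD and from 73.6% to 82.6% at 1 SD.

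A rank-based check on skewed whole-day stays, effect 0.6 SD, compared van Elteren with plain Wilcoxon: 60% vs 60% with no hip/knee difference, 61% vs 58% at 0.5 SD, and 61% vs 49% at 1 SD.

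**3. Binary outcomes.** 25 patients per stratum and arm, assumed odds ratio 0.3, 100,000 trials:

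| Hip / knee rate | Level: chi-square | Level: CMH | Power: chi-square | Power: CMH |
|---|---|---|---|---|
| 30% / 30% | 0.0122 | 0.0118 | 43.6% | 41.6% |
| 20% / 40% | 0.0111 | 0.0124 | 41.0% | 41.1% |
| 10% / 50% | 0.0059 | 0.0122 | 32.6% | 38.4% |

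Cochran-Mantel-Haenszel (CMH) holds its level throughout. It gains power only in the last row.

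**4. The open test choice, worst case.** If the smaller of the t-test and Wilcoxon P-values were always taken and hip and knee did not differ, the level per continuous outcome would be 0.0156 (normal), 0.0157 (lognormal, coefficient of variation 0.7) or 0.0162 to 0.0167 (whole-day stays). The four-outcome bound would be 2 × 0.0125 + 0.0156 + 0.0157 = 0.056, or 2 × 0.0125 + 0.0156 + 0.0167 = 0.057. With a hip/knee difference, the conservatism in step 2 offsets this: about 0.012 to 0.0135 at 0.5 SD, and 0.005 to 0.007 at 1 SD.

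**The case against.** The strongest reply is that an unstratified test after stratified randomisation is valid, only cautious, and that the size of the loss rests on hip/knee differences the documents never state. Both points stand. At 0.5 SD the loss is about 3 percentage points; only near 1 SD does it reach about 11. The even split is also the least favourable case, because the added variance p(1 − p)d² peaks at p = 0.5.

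A reader might infer more than the documents support, in four ways.

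- **That the 0.05 control is broken by ignoring the stratum.** It is not. A true level of 0.005 to 0.011 is below 0.0125, so the overall promise is kept with room to spare.
- **That the secondary confidence intervals are wrong.** Section 7.2 plans intervals for the two primary outcomes only. For secondary outcomes it specifies tests and a P-value criterion, so there is no planned interval to criticise.
- **That the either/or wording gives two chances at significance.** Nothing says the smaller P-value will be used. Asking for appropriate tests reads most naturally as a choice by distribution, and choosing by a Shapiro test on residuals gave levels of 0.011 (stays) and 0.0129 (normal). The 0.016 to 0.017 figure needs both the worst-case choice and no hip/knee difference, so it cannot be added to the power loss, which needs such a difference.
- **That power is also lost for nausea/vomiting and three-month pain.** This appears only when rates differ strongly by surgery type. At equal rates the stratified test costs about 2 points.

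It is also fair to say that van Elteren is one option among several. A linear model with surgery type serves QoR-15 equally well and yields an effect estimate.

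**Conclusion.** The point holds as a free improvement to the secondary analyses. The plan stratifies allocation by surgery type and then leaves that factor out of all four secondary tests. For the continuous outcomes the cost runs from nothing, if hip and knee are alike, to about 11 points of power at an assumed 1 SD difference. For the binary outcomes the case is consistency with the design and a level close to nominal, not a dependable gain in power. The unspecified choice between t-test and Wilcoxon is mainly missing detail, and the same edit resolves it. All sizes rest on the assumed hip/knee differences, event rates and treatment effects.

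**What to change.** In Section 7.2, before unblinding, name one test per continuous secondary outcome, adjusted for surgery type as randomised: for example van Elteren for length of stay, and van Elteren or a linear model with surgery type for QoR-15. This replaces the either/or wording.

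For nausea/vomiting and three-month pain, state whether the chi-square test stays or Cochran-Mantel-Haenszel by surgery type is used. The latter matches the design and keeps the level near 0.0125, at a possible cost of about 2 points of power if rates are similar in hip and knee.

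The 0.0125 criterion can stay. The cost is SAP wording only: surgery type is already recorded at randomisation, so no extra data, visits or patients are needed.

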2. STUDY OBJECTIVES

Primary and secondary objectives

The primary objective of this study is to compare the efficacy of gabapentin enacarbil 600 mg BID taken 1 day pre-op and approximately 2 hours before the surgery and restarted within 6 hours of completion of surgery and then 3 days post-operative versus placebo in reducing the use of opiates and/or pain scores in post-hip and knee arthroplasty surgery patients with spinal anesthesia.

Using a randomized design and blinded assessments, our goal is to determine whether Gabapentin enacarbil when used as a modality of pre-emptive analgesia decreased opioid consumption and/or decreased pain scores in hip and knee arthroplasty surgery.

The proposed research will have the following aims:

Primary objectives include:

Primary Aim 1: To assess whether gabapentin enacarbil decreases pain and/or opioid requirements after hip or knee surgery.

Hypothesis: Patients received gabapentin enacarbil will have less pain scores and/or less opioid consumption during the initial 72 hours after hip or knee surgery compared to patients who received placebo, and not worse on either outcome.

Secondary objectives include:

Secondary Aim 1: To assess whether gabapentin enacarbil decreases the incidence of persistent incisional pain three months after surgery when used as a modality of pre-emptive analgesia.

Hypothesis: Gabapentin enacarbil decreases the persistence of incisional pain three months after surgery.

Secondary Aim 2: To evaluate whether gabapentin enacarbil decreases nausea and vomiting during the initial 72 post-operative hours.

Hypothesis: The incidence of postoperative nausea and vomiting is reduced in patients given gabapentin enacarbil during the initial 72 hours after hip and knee replacement surgery.

Secondary Aim 3: To evaluate whether gabapentin enacarbil reduces the duration of hospitalization.

Hypothesis: The duration of hospitalization after knee or hip arthroplasties is reduced in patients given gabapentin enacarbil.

Secondary Aim 4: To evaluate whether gabapentin enacarbil will improve patient's satisfaction.

Hypothesis: Patients are more satisfied with the pain and quality of life after taking gabapentin enacarbil compared to placebo, as assessed using the quality of recovery score (QoR-15).

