7. STATISTICAL PLAN

7.1 Sample Size Determination

Sample size is fixed to be at 100 patients. We will recruit 100 patients having hip or knee arthroplasties with spinal anesthesia. 50 patients control will be given the placebo for five days and 50 patients will be given GEn 600 mg bid for five days.

Power consideration. Sample size is fixed to be at 100 patients. Power estimation is based on the analysis of superiority on opioid consumption because this analysis requires more patients than the superiority analysis on pain scores. As it is stated in the hypothesis to claim positive effect of gabapentin enacarbil at least on one of these outcomes should be superior. Assuming the pilot study recruited total 100 patients and coefficient of variation (SD/mean) of 0.7 for both groups, we would have about 90% power to detect the ratio of 0.63 in geometric means in opioid consumption (i.e., a geometric mean opioid consumption decreases more than 37% in gabapentin enacarbil patients) comparing gabapentin enacarbil patients to patients receiving placebo at significance level of 0.0125.

If the assumptions appear to be too optimistic and study turns out to be underpowered, nevertheless treatment effects and variability identified in this pilot investigation can be used to plan a future study with sufficient power.

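### Low priority, optional: Holm's step-down in place of single-step Bonferroni for the four secondary outcomes keeps the 0.05 familywise level and every Bonferroni claim, at the price of one sentence

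*Combined protocol and SAP*

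**What the plan says.** Section 7.2 (Statistical Methods) compares the groups on four secondary outcomes with two-sided superiority tests. Duration of hospitalization and QoR-15 are analysed by t-test or Wilcoxon rank sum test. Nausea and vomiting within 72 hours, and conversion from acute to chronic pain, are analysed by chi-square test.

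On multiplicity it states: "The significance level for the set of secondary outcomes will be preserved at 0.05 overall". Each test uses P < 0.05/4 = 0.0125, "applying a Bonferroni correction for multiple testing of the 4 secondary outcomes". No step-down is described, and no confidence interval rule is attached to these claims.

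The primary superiority step in the same section is a separate family. It "will be adjusted for multiple testing (two outcomes) via Bonferroni correction", and there "superiority will thus be claimed for a particular outcome if the 97.5% confidence interval is below zero".

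Section 2 gives each secondary aim its own hypothesis. Section 7.1 gives no effect size, event rate or power for any secondary outcome, and states: "Sample size is fixed to be at 100 patients".

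**The concern.** Single-step Bonferroni holds every secondary test at 0.0125 whatever happens to the other three. Once one outcome has been claimed, the remaining tests could be judged less strictly without exceeding 0.05 overall. The plan leaves that room unused.

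Because each secondary aim has its own hypothesis, the report will say which individual outcomes improved. What is at stake is therefore a second, third or fourth secondary claim. The primary conclusion, the effect estimates and the sample size are not affected.

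**Working it through.** **The plan's own figure.** 0.05/4 = 0.0125, which reproduces. The four thresholds sum to 4 × 0.0125 = 0.05, so the rule holds under any dependence. With four independent tests and no real effects the familywise error is 1 − (1 − 0.0125)^4 = 0.0491.

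**Holm's rule.** Order the P-values and compare them in turn with 0.05/4 = 0.0125, 0.05/3 = 0.0167, 0.05/2 = 0.025 and 0.05, stopping at the first failure. The first threshold equals Bonferroni's, so the chance of at least one claim is identical. Later thresholds are never lower than 0.0125, so no Bonferroni claim is lost.

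**Illustration.** Take P-values of 0.004, 0.015, 0.020 and 0.20. Bonferroni claims one outcome (0.004 < 0.0125). Holm claims three (0.004 < 0.0125, 0.015 < 0.0167, 0.020 < 0.025) and stops at 0.20 > 0.05. These values were chosen to fall where the two rules part, so the example does not show how often that happens.

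**How often it matters.** The inputs are assumptions: power per real effect of 30%, 60% or 80% at two-sided 0.05, with one to four real effects and independent tests. Four normal test statistics were simulated, with 2,000,000 draws per scenario.

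| Power at 0.05 | Per-test power, Bonferroni | Per-test power, Holm (1, 2, 3, 4 real effects) | Trials in which the claims differ (1, 2, 3, 4 real effects) |
|---|---|---|---|
| 30% | 14.4% | 14.5%, 14.8%, 15.2%, 15.7% | 0.3%, 1.1%, 2.5%, 4.6% |
| 60% | 38.8% | 39.0%, 40.5%, 42.5%, 45.5% | 0.7%, 4.1%, 11.0%, 21.8% |
| 80% | 62% | 62.1%, 64.5%, 67.7%, 72.7% | 1.0%, 6.4%, 17.5%, 35.2% |

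No Bonferroni claim was lost in any draw. With correlation 0.3 and 80% power, Holm's per-test power is 62.1%, 64.3%, 67.3% and 71.6%, so the picture hardly changes.

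**Which rows are plausible.** For the two chi-square outcomes, take 50 per arm and an assumed placebo event rate that is halved on active treatment. Exact enumeration of the Pearson test without continuity correction gives:
- 20% vs 10%: power 30.3% at 0.05 and 13.2% at 0.0125
- 30% vs 15%: 44.3% and 24.5%
- 40% vs 20%: 59.5% and 38.2%

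The lower rows of power are therefore the more plausible ones for these two outcomes.

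**The price in error.** With one, two or three real effects there are three, two or one true nulls. Bonferroni's familywise error is then 1 − 0.9875^3 = 3.7%, 1 − 0.9875^2 = 2.5% and 1.25% (simulated at 1.2% to 1.3%). Under Holm it becomes about 4.5%, 3.9% and 3.1% at 80% power, and 3.9%, 2.7% to 2.8% and 1.5% at 30% power. All are below 5%.

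With only one real effect, most of the added claims are false. At 80% power Holm adds about 0.15 true and about 0.83 false claims per 100 trials, so 0.83/(0.83 + 0.15) = 85% of the added claims are false. At 30% power it adds about 0.09 true and 0.22 false.

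**The case against.** The strongest case for leaving the text alone is that nothing is broken. The family, the number of tests, the overall level and the per-test threshold are stated and agree, and choosing between two valid procedures is the sponsor's decision. In the low-power scenarios that look likelier for the binary outcomes, the claims differ in fewer than 5% of trials. The larger gains need three or four real effects with good power, which nothing in the documents supports for 100 patients. Bonferroni also has simple matching simultaneous intervals, at 1 − 0.0125 = 98.75%, and Holm does not. Section 7.1 presents the trial as a pilot whose estimates may plan a later study, so intervals may matter more than an extra claim.

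Much of this stands, and it is why the point is low priority. It does not remove the point. For decisions made purely on P-values, Holm gives at least as many claims at the same error level, and Section 7.2 does not call for 98.75% intervals.

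Two stronger readings are tempting. The first is that the secondary error rate is not controlled or the threshold is wrong. The documents do not support that, since 0.05/4 is correct and sufficient. The second is that the primary superiority step should change in the same way. There each claim is read from a fixed 97.5% interval, so a step-down would make the interval for the second outcome depend on the result for the first. The primary success rule requires noninferiority "on both outcomes and superior on at least one of the outcomes", and the chance of superiority on at least one would be the same under either procedure. Keeping Bonferroni there is reasonable.

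**Conclusion.** This is a cheap improvement confined to the secondary family, not an error. Three properties hold without any assumption about effect sizes or correlation: the same 0.05 familywise level, no Bonferroni claim lost, and an unchanged chance of at least one claim.

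The size of the gain does rest on assumptions, because the documents supply no secondary effect sizes. It is about 0.1 percentage points of per-test power with one real effect. With four real effects it is about 1.3 points at 30% power (15.7% − 14.4%) and 10.7 points at 80% power (72.7% − 62%). A sponsor who prefers simultaneous intervals for the secondary outcomes could reasonably decline.

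**What to change.** In the secondary-outcome paragraph of Section 7.2, replace the fixed 0.0125 criterion with Holm's procedure: order the four P-values, compare them with 0.05/4, 0.05/3, 0.05/2 and 0.05 in turn, and stop at the first that fails. Leave the primary superiority step and its 97.5% interval rule unchanged.

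Timing matters. Section 8.6.1 has the Executive Committee reviewing data labelled Group A/B at intervals, including adverse events, and Section 3.3 treats nausea and vomiting as an opioid-related adverse event as well as a secondary endpoint. The change should therefore be fixed before anyone deciding it has seen data separated by group, or be made by people without access to that review. Specifying it before formal unblinding is not enough.

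The cost is one sentence, with no extra patients or data. The sponsor accepts that more of the permitted 5% is used (for example 1.2% rising to 3.1% with three real effects at 80% power), that added claims are mostly false if only one effect is real, and that simple matching simultaneous intervals are no longer available.
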